#### IV. RESEARCH STUDY DESIGN

Overview and Design of the Proposed Study

A sample of 289 patients who report chronic (at least 12 weeks) low back pain and the intention to try marijuana products for pain relief will be collected. Although the origin of chronic pain is heterogeneous and diagnostically complex, with subjective, affective, and cognitive components, self-report is the backbone of a medical diagnosis. Thus, we rely on self-report of pain intensity and duration for inclusion decisions for our study. Participants need to have at least one instance of lifetime marijuana use, but must have less than weekly marijuana use for the prior six months. Additionally, participants must not have used marijuana at *any time* for the treatment of their pain. As such, participants will be naïve to the use of marijuana for pain, but not to marijuana consumption in general. Recruitment will be via a number of sources that have been used successfully by our research team (described below). If the patient meets minimum eligibility criteria (also described below) and is interested in participating, they will set up an appointment to come to the CU Change Lab for their Baseline Appointment (1st Appointment) involving consent, extensive measures of health behavior (e.g., substance use, sleep quality, physical function, mood, health history, etc.), a blood draw to determine cannabinoid levels and biomarkers of inflammation, and baseline assessments of their low back pain and cognitive function.

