# **Specific Aim 1:**

# **Hypothesis 1**

**Objective 1:** We will observe levels of pain in individuals with chronic low back pain who engage in 2 weeks of *ad libitum* use of marijuana edible product of their choice with various cannabinoid content. *Hypothesis 1* predicts that observed THC and CBD blood levels will impact lower levels of low back pain interference after 2 weeks, compared to THC or CBD blood levels considered in isolation.

**Primary endpoint/analysis**: The Roland Morris Disability Questionnaire (RMDQ) has been used in studies of low back pain and asks participants about how their experience of low back pain interfered with 24 daily activities in the past two weeks; total score ranges from 0-24. Using the total RMDQ score, we will test pain interference using two time points – Baseline (prior to taking any cannabis) and 2-Week Pre-administration (after 2 weeks of product use but immediately before last edible use in the 2-Week study period). We will test a ordinary least squares (OLS) regression model in which blood levels of CBD, THC, and the CBDxTHC interaction are used to predict 2-Week pre-administration pain interference controlling for Baseline pain interference. Note that our participants are naïve to recent cannabis use at Baseline (per our eligibility criteria) so it is not necessary to control for Baseline levels of cannabinoids. Thus we are testing the effect of blood levels of cannabinoids on experience of recent pain interference. We predict that higher levels of THC and CBD will be associated with less pain interference.

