#### VI. ABOUT THE SUBJECTS

Ethnic diversity of this sample is expected to be representative of the greater Boulder-Denver area at large, such that approximately 20-30% of the final sample will represent Latino and non-Caucasian individuals. A trained research assistant will screen prospective participants who call, email, or complete an online survey, according to the inclusion/exclusion criteria below (Table 2). In order to increase consistency between our observational study and published clinical trials in low back pain patients, we will recruit individuals between 21 to 70 years of age with non-specific low back pain that has persisted at least 3 months. Given potential confounding influences on inflammatory markers (e.g., IL6, TNFa) and pain outcomes, we will exclude indviduals who report daily tobacco use, an immune-related disease (e.g., HIV), use of antivirals, steriods, psychotropic medications other than anti-depressant SSRIs and ADHD stimulant and non-stimulant medications, or maximal doses of NSAIDs. Use of opiates, anti-depressants, ADHD medications, menstrual cycles, and birth control will be tracked during the study. Specific criteria for study participants are listed in Table 2 below.

Table 2. Inclusion/Exclusion criteria.	
Inclusion	Exclusion
Self-reported low back pain ≥ 3 months	Low back pain with pain intensity rated at less than 4 and pain interference with activities rated at less than 3 (on 1-5-point scales)
At least one episode of lifetime marijuana use, but	More than weekly use of marijuana in prior six months, or
less than or equal to weekly marijuana use for prior	use of marijuana to treat their low back pain at any time in
six months	their lives
Intent to initiate use of marijuana to treat their low	Actively seeking or in treatment for any substance use
back pain	disorder; Report of drug use in past 72 hours before Baseline

	Appointment (other than opiates) or failed urine screen (e.g., cocaine, methamphetamine, etc.).
21-70 years of age	Daily tobacco use (cigarette, E-cigs, and smokeless)
Able to provide informed consent	Current diagnosis of bipolar disorder or schziophrenia, use of psychotropic medications (other than SSRIs and ADHD meds), antivirals, steriods, or maximal doses of NSAIDs
Health eligibility approved by study physician when applicable	Acute illness other than low back pain or any immune-related disease (e.g., HIV; See excluded illness list below.)

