## **Baseline Appointment Procedure and Assessments**

Subjects who meet inclusion criteria (see Table 2 above) will be scheduled for a Baseline Appointment and given instructions, including not consuming alcohol for 24 hours, tobbacco, caffeine, and any other drugs for 72 hours (excluding those needed for regular pain management) prior to the appointment. Subjects will be reminded to eat a small meal and hydrate well before the baseline appointment. After arriving at the CUChange Laboratory, each subject will go through the consent process and after all questions have been answered and if participants consent, Baseline procedures will begin (see Table 3). A urine toxicology and a pregancy test (for females) will also be administered to verify if subjects have recently taken illicit drugs and to ensure that they are not pregnant. A blood draw will be taken to quantify current use of cannabinoids and inflammatory markers (1st of 4 total blood draws completed during the entire study). All blood draw procedures performed during this study will involve collecting venous blood (40 mL per draw) with venipuncture of a peripheral arm vein using standard, sterile phlebotomy techniques. Subjects will then complete current and historical health and substance use assessments (see section below and Table 3 for details), and a motor and cognitive testing battery.

At the end of the Baseline Appointment, individuals will be asked to self-select an edible marijuana product based on their preference. Participants will then use their selected product at home, consistent with the packaging directions, direction from their physician, or as they see fit, and will be asked not to use any other marijuana product during the 2-Week study period, before their 2-Week Appointment

(Mobile Laboratory assessment). Study staff will not provide any directions regarding dosing and self-administration. While participants themselves will not be blind to their product choice, importantly, the researchers who conduct the assessments as well as most of the senior investigators will be blind to their selection. At the Baseline Appointment, participants will be given instructions and allowed to practice responding to an online daily message prompt (described below), that will commence after they purchase an edible of choice.

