## Monthly (Online-based) Follow-up Assessments

After the 2-Week *ad libitum* period of edible use with detailed online and in-person tracking, participants will be asked to provide monthly follow-up information on their pain and marijuana use. All subjects will be given extensive instructions on completing the daily message report at the Baseline Appointment and will practice answering the questions in the lab using their cell phone or a lab computer to ensure they understand the process and time commitment. They will answer online survey assessments with individually tailored links hosted by our university's licensed survey tool RedCap. To track participant behavior and potential effects (e.g., marijuana use and pain levels) naturalistically, a monthly survey will assess self-reported marijuana use, sleep, pain ratings and management, and cognitive effects over the past month, for the six months. To enhance the response rate, participation on monthly follow-ups will be monitored and participants will be contacted if they if they do not respond to one monthly survey. Participants will receive a \$5 gift card by mail for every monthly online follow-up survey that they complete, plus a \$10 bonus gift card for the final survey (\$40 in total possible).

Please see Table 3 for a detailed description of the procedures and measure by appointment and Table 4 (page 26) for a Schedule of Evaluations.

Table 3. Description of observation		
•		
Name of Instrument/Procedure	Data collected	
Eligibility Screening (ES)	Phone Interview or Online Survey questionnaire used to	
	determine subject eligibility (based on Table 2	
	inclusion/exclusion criteria).	
Baseline Appointment (only)		
Informed Consent (IC)	In-person discussion and review of consent document detailing	
imormed Consent (IC)	all observational measures and any questions.	
Medical History (MH)	General assessment of medical history for any major disease or	
ivicultal filstory (ivili)	illness, the neuropathic pain scale, and prescribed medication	
	use.	
Toxicology Drug Screening (TDS)	A urine sample will test for recent substance use (e.g.,	
	marijuana, cocaine, benzodiazepines, MDMA, sedatives, or	
	methamphetamine) other than pain medications.	
Pregnancy Screening (PS)	All female participants will take a urine pregnancy test and	
	report their last menstrual cycle and any birth control methods.	
Demographics (D)	Age, sex, marital status, race/ethnicity, education, birth date,	
	and height.	

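### H1 omits prior cannabis use because eligibility is said to make participants naive to recent use, but the only explicit drug-free window is 72 hours and the baseline RMDQ recalls two weeks

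*Combined protocol and SAP*

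**What the plan says.** The primary H1 model (Statistical Analysis Plan, Hypothesis 1) is an OLS regression of two-week pre-administration RMDQ on THC, CBD, their product and baseline RMDQ. It has no term for earlier cannabis exposure, and the stated reason is this: "our participants are naïve to recent cannabis use at Baseline (per our eligibility criteria) so it is not necessary to control for Baseline levels" (the levels meant are blood cannabinoids). The same section describes the baseline time point as coming before any cannabis is taken. The H2 primary, H2 secondary and H3 primary analyses repeat both statements.

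The passages that should support this read differently:

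- Overview and Design: "participants will be naïve to the use of marijuana for pain, but not to marijuana consumption in general", and participants qualify "but must have less than weekly marijuana use for the prior six months".
- Table 2, inclusion: "less than or equal to weekly marijuana use for prior" six months. The matching exclusion is use more often than weekly.
- Table 2, exclusion: "Report of drug use in past 72 hours before Baseline", continuing "Appointment (other than opiates) or failed urine screen (e.g., cocaine, methamphetamine, etc".
- Baseline Appointment instructions: abstain from "any other drugs for 72 hours (excluding those needed for regular pain management").
- Table 3, toxicology: "A urine sample will test for recent substance use (e.g".), with marijuana in the list that follows.
- Table 3, RMDQ: recall is two weeks, changed from the instrument's usual single day.
- Table 3, TLFB: daily substance use is recorded for the two weeks before Baseline.

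**The concern.** The omission rests on a premise about eligibility, and the eligibility criteria do not deliver it. The plan does not define recent. If it means the last three days, the premise may hold for blood levels but not for a pain-interference score that looks back 14 days. If it means the recall period, the criteria do not assure it.

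This matters because exposure is self-chosen. Participants select the product and the amount, and prior use could plausibly be related to both. If prior use is related to the two-week THC or CBD level and also affects the baseline score, adjusting for that score does not remove the problem. It can create a spurious association between level and outcome. H1 would then report a main-effect coefficient that partly reflects who had been using cannabis before Baseline.

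**Working it through.** **1. The plan's own figure.** N = 246, f² = 0.04, two-tailed alpha 0.05, three predictors. Testing one coefficient: noncentrality = 246 × 0.04 = 9.84, with 246 − 3 − 1 = 242 degrees of freedom. Power is 0.878, which matches the stated .88.

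**2. How much of the recall window is covered.** 14 days minus 3 days (72 hours) leaves 11 days, or 11/14 = 79%, with no stated abstinence.

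**3. How many uses fit.** Count Baseline as day 0, with the last use on day −4 and even spacing.

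| Spacing (days) | Uses within days −14 to −1 |
|---|---|
| 7 (allowed by Table 2 only) | −4, −11 |
| 8 | −4, −12 |
| 9 | −4, −13 |
| 10 | −4, −14 |
| 11 or more | −4 only |

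Two uses fit under either frequency rule. The average is lower. An evenly spaced weekly user has 11/7 = 1.57 uses in the 11 days. Assumed rates of 0.25 to 0.9 per week, which satisfy the less-than-weekly rule, give 0.4 to 1.4.

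**4. Whether baseline RMDQ adjustment is enough.** All inputs in this step are assumed, for illustration. A stable interference score has SD 5 (variance 25). Reliability of 0.8 gives an error variance of 25 × 0.2/0.8 = 6.25 at each visit. Prior use (standardised) shifts baseline RMDQ by g points per SD, correlates ρ with the two-week level, and has no effect at two weeks. The true effect of the level is zero. The coefficient of the level, adjusted for baseline RMDQ, is then

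b = −25ρg / (31.25 + g² − ρ²g²).

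| ρ | g | b (RMDQ points per SD) |
|---|---|---|
| 0 | any | 0 |
| 0.2 | −0.5 | 2.5/31.49 = 0.08 |
| 0.2 | −1 | 5/32.21 = 0.16 |
| 0.4 | −0.5 | 5/31.46 = 0.16 |
| 0.4 | −1 | 10/32.09 = 0.31 |

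A simulation of the same set-up gave 0.09, 0.15, 0.15 and 0.31, and about 0 in every case once prior use was in the model. The sign is positive: a higher level appears to go with more interference, against H1.

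For scale, the residual variance given baseline is about 31.25 − 25²/31.25 = 11.25. The standard error at N = 246 is therefore about √(11.25/246) = 0.21 points.

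**5. Cost of the covariate.** With baseline RMDQ and TLFB use days there are five predictors and 240 degrees of freedom. Noncentrality is 9.84 × (1 − R²), where R² is the share of the tested term's variance explained by the added covariate (assumed).

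| R² | Noncentrality | Power |
|---|---|---|
| 0 | 9.84 | 0.878 |
| 0.01 | 9.74 | 0.875 |
| 0.04 | 9.45 | 0.865 |
| 0.09 | 8.95 | 0.846 |
| 0.196 | 7.91 | 0.800 |
| 0.20 | 7.87 | 0.798 |

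**The case against.** The best defence is that the sentence speaks of blood levels, and its conclusion about those is probably right. The protocol itself says oral cannabinoid levels drop off rapidly by four hours after ingestion, so levels after 72 hours are likely low. That stands. A reader might infer that baseline THC and CBD ought to be covariates, but the documents do not support that. What is left out is use during the recall period, which a blood sample taken at the visit would largely miss.

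Second, 72 hours may not be the true limit. Urine is tested at Baseline, the panel lists marijuana, and a failed screen excludes. If a marijuana-positive result is a fail, the assured window could be longer. This also stands in part: 72 hours is the only explicit window, not a proven bound. But the Table 2 examples do not name marijuana, the Baseline section describes the test as a check for illicit drugs, and nothing says that a marijuana-positive result excludes.

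Third, two uses is a ceiling and none of that use was for back pain. Both are correct. The share of participants with any use in the window is not given.

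Fourth, a reader might attach a false-positive rate to H1. A generic omitted-variable calculation can produce such rates, but they rest wholly on assumed correlations and do not model the recall mechanism. Where that mechanism is modelled alone, the bias runs against the hypothesis. The documents give no basis for claiming spurious support for H1.

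Fifth, H2 and H3 are measured at the visit and have no two-week recall, so their case is weaker. For them the issue is use history or carry-over; the Background says cognitive impairment may persist for hours to days. That supports a sensitivity analysis rather than a change to the primary model.

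**Conclusion.** The concern holds for H1. The stated reason for leaving out earlier exposure is not supported by the eligibility criteria, and the description of Baseline as preceding all cannabis is not assured. What the protocol supports is that Baseline comes before the participant buys and starts the chosen product (Marijuana Administration at Home).

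The THC and CBD main-effect coefficients can be biased despite baseline RMDQ adjustment, provided prior use is related to the two-week level. If it is not, the mechanism shown gives no bias. If prior use lowers baseline RMDQ and does nothing else, the bias is against the hypothesis. If prior use also predicts the two-week outcome directly, the direction is open. The illustrative 0.08 to 0.31 RMDQ points per SD rests entirely on assumed inputs, so the size in this study is unknown.

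It would be too strong to read this as an error in the stated power or sample size, as a finding about the interaction test, or as evidence that typical participants used cannabis twice before Baseline. The point is worth fixing because the remedy uses data already collected and costs little.

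**What to change.** - **Justification.** In the H1 primary, H2 primary, H2 secondary and H3 primary analyses, replace the statement about naivety. Say that baseline blood levels are expected to be low after the 72-hour window and that prior use is handled as below. Reword the description of Baseline to say that it precedes the start of the chosen product.
- **H1.** Add the number of TLFB cannabis use days in the two weeks before Baseline as a prespecified covariate. It covers the same window as the baseline RMDQ. Report the model without it alongside.
- **H2 and H3.** Fit the same covariate as a prespecified sensitivity analysis.
- **Reconcile.** Align the frequency limit in Overview and Design (less than weekly) with Table 2 (up to and including weekly). State whether a marijuana-positive urine result counts as a failed screen, since Table 2 and Table 3 leave this open.

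The cost is SAP wording and one degree of freedom, with no new data. Power is unchanged at 0.878 if the covariate is unrelated to the tested term, about 0.846 at 9% overlap, and above the 0.80 target until overlap reaches about 19.6%, a correlation of √0.196 = 0.44. The Interim Analyses section defers hypothesis tests until the dataset is locked, so the change can be specified before then.

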# **Hypothesis 2**

**Objective 2:** To observe levels of circulating cytokines in individuals with chronic low back pain who engage in 2 weeks of *ad libitum* use of marijuana edibles with various cannabinoid content. *Hypothesis 2* predicts that THC and CBD blood levels will additively impact lower levels of circulating cytokines after 2 weeks and after a single use compared to THC or CBD blood levels considered in isolation.

**Primary endpoint/analysis**: Using the levels of four *individual* circulating cytokines (TNF $\alpha$ , IL-6, IL-8, IL-1B) after two weeks, we will test level of recent inflammation using two time points: a) Baseline

(prior to taking any cannabis) and b) Pre-administration (after two weeks of product use but immediately before the last edible use in the 2-Week study period). We will test an OLS regression model model in which blood levels of CBD, THC, and the CBDxTHC interaction are used to predict pre-administration inflammation controlling for baseline inflammation. Note that our participants are naïve to recent cannabis use at baseline (per our eligibility criteria) so it is not necessary to control for baseline levels of cannabinoids. Thus we are testing the effect of blood levels of cannabinoids on recent inflammation. We predict that higher levels of THC and CBD will be associated with lower levels of inflammation, and that there will be interactive effects such that those participants with the highest levels of both THC and CBD will experience the lowest levels of inflammation.

**Secondary analysis/endpoint:** Average Z-scored value for the panel of circulating inflammatory markers (IFNg, IL-1a, IL-1b, IL-6, IL-2, IL-4, IL-8, IL-10, IL-12, and TNFα). Using the average of our panel of inflammatory markers, we will test level of recent inflammation using two time points: a) Baseline (prior to taking any cannabis) and b) Pre-administration (after two weeks of product use but immediately before final edible use in the 2-Week study period). We will test an OLS regression model in which blood levels of CBD, THC, and the CBDxTHC interaction are used to predict pre-administration inflammation controlling for baseline inflammation. Note that our participants are naïve to recent cannabis use at baseline (per our eligibility criteria) so it is not necessary to control for baseline levels of cannabinoids. Thus we are testing the effect of blood levels of cannabinoids on recent inflammation. We predict that higher levels of THC and CBD will be associated with lower levels of inflammation, and that there will be interactive effects such that those participants with the highest levels of both THC and CBD will experience the lowest levels of inflammation.

# **Specific Aim 2:**

# **Hypothesis 3**

**Objective 3:** To observe cognitive function in individuals with chronic low back pain who engage in 2 weeks of *ad libitum* use of marijuana edibles with various cannabinoid content. *Hypothesis 3* predicts that THC blood levels will dose-dependently impact poorer verbal recall and selective attention after 2 weeks, whereas the CBD bloods will attenuate cognitive impairment.

Primary endpoint/analysis: Age and sex-corrected scores from the Flanker Inhibitory Control and Attention task (FICA) and the NIH toolbox cognitive battery and delayed Verbal Recall Memory from the International Shopping List Task are our co-primary outcomes. We will test level of recent cognitive impairment using two time points – Baseline (prior to taking any cannabis) and Pre-administration (after 2 Weeks of product use but immediately before the last edible use in the 2-Week study period). We will test an OLS regression model model in which blood levels of CBD, THC, and the CBDxTHC interaction are used to predict Pre-administration cognitive impairment controlling for Baseline cognitive impairment. Note that our participants are naïve to recent cannabis use at Baseline (per our eligibility criteria) so it is not necessary to control for Baseline levels of cannabinoids. Thus we are testing the effect of blood levels of cannabinoids on recent cognitive impairment. We predict that higher levels of THC and lower levels of CBD will be associated with higher levels of cognitive impairment, and that there will be interactive effects such that those participants with the highest levels of THC and the lowest levels of CBD will experience the highest levels of cognitive impairment.

**Secondary analysis/endpoint:** Using our co-primary measures of cognitive impairment listed above, we will test acute effects of cannabinoids on cognitive impairment at the 2-Week Appointment, using three time points: a) Pre administration (before the last edible use), b) Post-1h administration (1 hour after the last edible use), and c) Post 2h administration (2 hours after the last edible use) of the 2-week ad libitum study period. We will test an OLS regression model in which changes in blood levels of CBD, THC, the CBDxTHC interaction, time (pre-administration, 1hour post administration and 2 hours post administration) and all possible interactions are used to predict acute changes in cognitive impairment. All independent variables in this analysis are within-subjects as they occur over time. Thus we are testing

the effect of changes in blood levels of cannabinoids on changes in acute cognitive impairment. We predict that greater increases in THC and smaller increases in CBD acutely will be associated with greater increases in cognitive impairment, and that there will be interactive effects such that those participants with the greatest increases in THC and the smallest increases in CBD will experience the greatest increases in acute cognitive impairment.

Another secondary endpoint includes the total score from the self-reported subjective cognitive functioning from the Functional Assessment of Cancer Therapy – Cognitive Function (FACT-Cog) scale, which assesses perceived cognitive impairments, abilities, and quality of life.

